7 DATA ANALYSIS

Descriptive statistics will be provided to summarize outcomes at each visit as well as for change from baseline. Continuous endpoints will be summarized with N, mean, standard deviation, minimum, maximum, and median. Categorical or binary endpoints will be summarized by count and percentage. Analysis of covariance (ANCOVA) will be used to assess the treatment effect between baseline and 4 weeks for iLux and LipiFlow (LF) treatments for the primary and secondary effectiveness endpoints. For each endpoint analyzed, the baseline value will be used as a covariate.

Given that non-inferiority is demonstrated for the iLux endpoints, success will not be claimed unless the mean change from baseline in the test arm is clinically significant and significantly different from

zero. For any endpoints for which non-inferiority is demonstrated and mean changes from baseline are clinically significant and significantly different from zero, a test for superiority will be performed.

All subjects enrolled and treated in the study shall be included as part of the safety analysis.

Subjects who are randomized but not treated for any reason will be included in the intent-to-treat analysis as part of the arm to which they are randomized but they will be excluded from the per-protocol analysis.

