7.2 Non-Inferiority Compared to Control

7.2.1 Primary Effectiveness Endpoints Hypothesis

7.2.1.1 MGS

The co-primary effectiveness endpoint, MGS, will be tested for non-inferiority against LipiFlow using a 5-point non-inferiority delta (δ) in a one-tailed test.

It is hypothesized that the MGS mean score from the iLux group will not be lower than (not inferior to) the MGS mean score from the LipiFlow group at the 4-week exam:

Null Hypothesis: $\mu (\text{iLux-MGS} - \text{LF-MGS}) + \delta \leq 0$

Alternate Hypothesis: $\mu (\text{iLux-MGS} - \text{LF-MGS}) + \delta > 0$

Where $\mu (\text{iLux-MGS} - \text{LF-MGS})$ is the mean difference in the MGS between iLux and LipiFlow from baseline to week 4 and $\delta = 5$.

The MGS was found to be highly correlated across eyes in the previously completed pilot study data (correlation of 0.68); consequently, OD and OS values will be averaged to form an overall person score. An ANCOVA model, with baseline MGS as a covariate, will be used to assess the difference between the LipiFlow System and the iLux System results. The lower boundary of the least square means group confidence interval will be tested against the non-inferiority boundary of 5 points. To be successful, the lower boundary of the confidence interval must exceed -5.

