7.2.3 Multiplicity

Both co-primary endpoints, MGS and TBUT, must be successful to demonstrate non-inferiority. The secondary endpoint is only tested if the co-primary effectiveness endpoints are non-inferior.

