7.2.4 Sample Size Justification

The proposed sample size is 256 eyes (128 subjects) for this open-label, prospective multicenter trial designed to demonstrate non-inferiority of treatment with iLux relative to treatment with LipiFlow for the primary effectiveness endpoint. A total of 142 subjects is requested to allow for 10% fallout during patient screening. This study design provides a combined power of 88% to demonstrate non-inferiority given the following primary endpoint assumptions:

- MGS non-inferiority delta of 5 points and standard deviation of 8 points, provides a MGS primary endpoint power of 93.9%.
- TBUT non-inferiority delta of 2.5 seconds and standard deviation of 4 seconds, provides a TBUT primary endpoint power of 93.9%
- Power that both endpoints are significant, assuming independence, is $0.939^2 = 0.882$, or 88.2% power.

For the secondary endpoint, a standard deviation of 14 is assumed based on pilot data and the non-inferiority delta is set to 7. The chosen sample size and $\alpha = .025$ provides 80% power for this endpoint.

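### Up to three superiority tests have no stated alpha, order or adjustment; at one-sided 0.025 each, the chance of a false superiority claim could reach about 7%

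*Combined protocol and SAP*

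**What the plan says.** Section 7 (Data Analysis) applies ANCOVA to the primary and secondary effectiveness endpoints. It then sets the condition for superiority testing: "For any endpoints for which non-inferiority is demonstrated and mean changes from baseline are clinically significant" and also significantly different from zero, "a test for superiority will be performed". The sentence stops there.

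Section 7.2.3 (Multiplicity) has two sentences: "Both co-primary endpoints, MGS and TBUT, must be successful to demonstrate non-inferiority", and "The secondary endpoint is only tested if the co-primary effectiveness endpoints are non-inferior". Neither mentions superiority.

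Alpha is written once, in section 7.2.4, in the power statement for OSDI non-inferiority: "The chosen sample size and $\alpha = .025$ provides 80% power for this endpoint". Section 7.2.1.1 describes the MGS comparison as "using a 5-point non-inferiority delta (δ) in a one-tailed test", and 7.2.1.2 does the same for TBUT with its own margin. No alpha or sidedness is given for superiority.

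**The concern.** The trigger is worded per endpoint and Section 7 covers three of them, so up to three superiority tests can be made. Any one of them, if positive, would support a statement that the new device beats the marketed control.

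The existing conditions do not limit the error across endpoints:

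- **Non-inferiority first.** An endpoint that rejects for superiority has already cleared its non-inferiority margin. This step protects within an endpoint, not across endpoints.
- **Change from baseline.** These conditions are within-arm. They are met whenever the test device works, whether or not it differs from the control.
- **Both co-primaries must succeed.** This protects the non-inferiority claim, which needs both. A superiority claim could rest on any one endpoint.

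What is at stake is the credibility of any superiority statement. The trial is open-label and the protocol requires a masked rater only for MGS, so two of the three routes run through TBUT, with no masking stated, and subject-reported OSDI.

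**Working it through.** **Inputs.** From 7.2.4: 128 subjects (64 per arm at 1:1); MGS margin 5, SD 8; TBUT margin 2.5 s, SD 4 s; OSDI margin 7, SD 14; stated power 93.9%, 93.9% and 80%; independence assumed for the co-primaries. No correlation between endpoints is given, so a range is shown.

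**Step 1: the plan's own power, to find its alpha.** The standardised margin is margin / (SD × √(2/64)).

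- MGS: 5 / (8 × 0.1768) = 3.536. TBUT gives the same value. Power at one-sided 0.025 is 94.2% (normal) or 93.9% (noncentral t, 126 df).
- OSDI: 7 / (14 × 0.1768) = 2.828. Power is 80.7% (normal) or 80.1% (t).
- Both co-primaries: 0.939² = 88.2%.

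The stated figures reproduce. One-sided 0.05 would give 96.9% for MGS and TBUT, so the plan's non-inferiority tests were sized at one-sided 0.025. That level is carried over to superiority as an assumption.

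**Step 2: false superiority claims, no true difference, independent endpoints.** Let q = 0.025 be the chance of a false superiority result on one endpoint and p = 0.939 the chance of passing non-inferiority. The baseline-change conditions are taken as met.

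- Co-primaries only: 1 − 0.975² = 4.9%.
- Three tests, no gate: 1 − 0.975³ = 7.3%.
- Three tests, OSDI reached only if both co-primaries are non-inferior (7.2.3): 1 − [(1−q)² − (p−q)² × q] = 1 − [0.950625 − 0.914² × 0.025] = 1 − [0.950625 − 0.020885] = 7.0%.

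**Step 3: where the excess comes from.**

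- Superiority on one co-primary while the other fails non-inferiority: 2 × 0.025 × (1 − 0.939) = 0.3%.
- All superiority tests held until both co-primaries are non-inferior: p² − (p−q)² × (1−q) = 0.8817 − 0.8354 × 0.975 = 6.7%.

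Closing the route past a failed co-primary moves 7.0% to 6.7%. The remainder comes from unadjusted parallel tests.

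**Step 4: correlation.** Common correlation among the three test statistics, by numerical integration, OSDI gate as written:

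| Correlation | Three endpoints | Co-primaries only |
|---|---|---|
| 0 | 7.0% | 4.9% |
| 0.3 | 6.8% | 4.8% |
| 0.5 | 6.3% | 4.5% |
| 0.7 | 5.5% | 4.2% |
| 0.9 | 4.2% | 3.5% |
| 1 | 2.5% | 2.5% |

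**Step 5: a less favourable truth.** If TBUT is truly inferior by its full margin and the other endpoints do not differ (independent endpoints), the total is about 2.6%. A false TBUT superiority result is then nearly impossible and OSDI is rarely reached.

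**Step 6: the remedy.** In a fixed sequence, a false claim requires rejecting the first true null in the order at 0.025, so the error is at most 2.5%. Holm has the same bound. For comparison, Bonferroni at 0.025/3 with the OSDI gate gives about 2.4% under independence.

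**The case against.** The strongest reply is that this is a non-inferiority trial. Its hypotheses and sample size all concern non-inferiority, there is no superiority hypothesis or power calculation, and no labelling claim is mentioned. That stands as a limit on consequence: the type I error of the non-inferiority conclusion is not affected. It does not remove the gap, because Section 7 commits to the superiority tests.

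A second reply is that 7% sits at the top of the range. That also stands. It needs OSDI, a secondary endpoint already gated on both co-primaries, and it needs near-independence, whereas the three endpoints are measured in the same subjects. With positive correlation below 1 the rate falls but stays above 2.5%.

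A third is that the plan never says each superiority test uses the full 0.025. Correct: that level is inferred. The missing level is part of the problem.

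A reader might go further and infer that the plan allows superiority on one co-primary in a trial that failed on the other, and that this drives the inflation. The documents do not support this. Section 7.2.3 requires both co-primaries for non-inferiority to be demonstrated, and Section 7 opens superiority only where it is demonstrated. Read together, they may already block that route; read literally, the per-endpoint wording leaves it open. The text is ambiguous, not plainly contradictory. Even if the route is open, it contributes only about 0.3 points.

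**Conclusion.** The point holds as a gap in multiplicity control for the superiority tests. With no true difference and one-sided 0.025 per test, the chance of at least one false superiority claim is up to about 7% for three endpoints and up to 4.9% for the co-primaries alone, against 2.5%. Moderate to strong positive correlation (0.5 to 0.7) brings the three-endpoint figure to 6.3% to 5.5%.

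These figures rest on the assumed alpha, on the baseline-change conditions being met, and on correlations the documents do not give. It would be wrong to read 7% as the plan's actual error rate, or to conclude that the non-inferiority result is at risk. The matter should be corrected before analysis, but it does not threaten the primary objective.

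**What to change.** In Sections 7 and 7.2.3:

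1. State that superiority is tested only after both co-primaries have succeeded. This settles how the two sections fit together, but does little for the error rate by itself.
2. Test superiority in a fixed order, for example MGS, then TBUT, then OSDI, each at one-sided 0.025, stopping at the first failure. Holm across the three is an alternative. This is the step that brings the error to 2.5% or less.
3. Label any other superiority p-value as descriptive.

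The cost is about two sentences, with no change to the sample size or to the non-inferiority tests. The downside of the fixed order is that a superiority claim on a later endpoint is lost if an earlier one fails. Holm avoids choosing an order, but the smallest p-value must then meet 0.025/3 = 0.0083.

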7.1 Clinically Significant Effects

The values for clinical significance are used to establish the non-inferiority margins.

7.1.1 Meibomian Gland Score (MGS)

The clinical significance of the MGS score change both from baseline and in comparing study arms is based on a severity ranking using an alternative scoring method established by the consensus of clinical experts in the Diagnosis Subcommittee of the International Workshop on Meibomian Gland Dysfunction [4]. A difference in score of 5 changes the staging of the severity of MGD, and therefore represents a clinically significant level.

7.1.2 Tear Break-Up Time

The clinical significance for a change in TBUT both from baseline and in comparing study arms has not been reported in any of the published LipiFlow studies or other studies of MGD diagnosis and treatment. As a result, the clinical significance of the TBUT is based on labeling for the DET test strip (Table 2). The diagnosis of dry and abnormal tear stability is determined by a span of 5 seconds. If we use a moderate change in effect of 50%, then a difference in TBUT of 2.5 seconds is determined to be clinically significant. Based on this determination of a clinically significant change, a value of 2.5 seconds for the non-inferiority margin is used for TBUT primary endpoint.

Table 2: AMCON DET strip labeling

TBUT (seconds)	Significance
≥ 10	Normal
> 5 to < 10	Borderline dry eye
< 5	Dry eye

7.1.3 OSDI

A change in score of 7 is the minimal clinically significant difference for patients with moderate and severe dry eye established in a clinical study by Miller [9] using an anchor-based method. For this study, this value is being used both from baseline and in comparing study arms.

7.2 Non-Inferiority Compared to Control

7.2.1 Primary Effectiveness Endpoints Hypothesis

7.2.1.1 MGS

The co-primary effectiveness endpoint, MGS, will be tested for non-inferiority against LipiFlow using a 5-point non-inferiority delta (δ) in a one-tailed test.

It is hypothesized that the MGS mean score from the iLux group will not be lower than (not inferior to) the MGS mean score from the LipiFlow group at the 4-week exam:

Null Hypothesis: $\mu (\text{iLux-MGS} - \text{LF-MGS}) + \delta \leq 0$

Alternate Hypothesis: $\mu (\text{iLux-MGS} - \text{LF-MGS}) + \delta > 0$

Where $\mu (\text{iLux-MGS} - \text{LF-MGS})$ is the mean difference in the MGS between iLux and LipiFlow from baseline to week 4 and $\delta = 5$.

The MGS was found to be highly correlated across eyes in the previously completed pilot study data (correlation of 0.68); consequently, OD and OS values will be averaged to form an overall person score. An ANCOVA model, with baseline MGS as a covariate, will be used to assess the difference between the LipiFlow System and the iLux System results. The lower boundary of the least square means group confidence interval will be tested against the non-inferiority boundary of 5 points. To be successful, the lower boundary of the confidence interval must exceed -5.

7.2.1.2 TBUT

The co-primary endpoint, Tear Break-Up Time (TBUT) will be tested for non-inferiority against LipiFlow using a 2.5-second non-inferiority delta (δ) in a one-tailed test. A similar ANCOVA model will be used to compare TBUT between devices, with covariate adjustment for baseline TBUT. It is hypothesized that the TBUT mean time for the iLux group will not be less than (not inferior to) the TBUT mean time for the LipiFlow group at the 4-week exam:

Null Hypothesis: $\mu (\text{iLux-TBUT} - \text{LF-TBUT}) + \delta \leq 0$

Alternate Hypothesis: $\mu (\text{iLux-TBUT} - \text{LF-TBUT}) + \delta > 0$

Where $\mu (\text{iLux-TBUT} - \text{LF-TBUT})$ = mean difference in the TBUT between iLux and LipiFlow from baseline to week 4 and $\delta = 2.5$.

7.2.2 Secondary Effectiveness Endpoint Analysis

If the co-primary effectiveness endpoints demonstrate non-inferiority, the secondary effectiveness endpoint, change from baseline in Ocular Surface Disease Index (OSDI) at the 4-week exam, will be compared against the control device to test for non-inferiority. A similar ANCOVA model will be used to compare OSDI between devices, with covariate adjustment for baseline OSDI.

It is hypothesized that the OSDI mean score from the iLux group will not be lower than (not inferior to) the OSDI mean score from the LipiFlow group at the 4-week exam:

Null Hypothesis: $\mu (\text{iLux-OSDI} - \text{LF-OSDI}) - \delta \geq 0$

Alternate Hypothesis: $\mu (\text{iLux-OSDI} - \text{LF-OSDI}) - \delta < 0$

Where $\mu (\text{iLux-OSDI} - \text{LF-OSDI})$ = mean difference in the OSDI between iLux and LipiFlow from baseline to week 4 and $\delta = 7$.

7.2.3 Multiplicity

Both co-primary endpoints, MGS and TBUT, must be successful to demonstrate non-inferiority. The secondary endpoint is only tested if the co-primary effectiveness endpoints are non-inferior.

7.2.4 Sample Size Justification

The proposed sample size is 256 eyes (128 subjects) for this open-label, prospective multicenter trial designed to demonstrate non-inferiority of treatment with iLux relative to treatment with LipiFlow for the primary effectiveness endpoint. A total of 142 subjects is requested to allow for 10% fallout during patient screening. This study design provides a combined power of 88% to demonstrate non-inferiority given the following primary endpoint assumptions:

- MGS non-inferiority delta of 5 points and standard deviation of 8 points, provides a MGS primary endpoint power of 93.9%.
- TBUT non-inferiority delta of 2.5 seconds and standard deviation of 4 seconds, provides a TBUT primary endpoint power of 93.9%
- Power that both endpoints are significant, assuming independence, is $0.939^2 = 0.882$, or 88.2% power.

For the secondary endpoint, a standard deviation of 14 is assumed based on pilot data and the non-inferiority delta is set to 7. The chosen sample size and $\alpha = .025$ provides 80% power for this endpoint.

7.2.5 Safety Endpoints

The primary safety endpoint is the comparison of the incidence of device-related adverse events (e.g., changes in the lid margin, development of floppy eyelids, entropion or ectropion; and lash integrity) for the two treatments. The reporting period is from baseline through the last study visit.

The secondary safety endpoint is the evaluation of discomfort and pain during treatment and changes from baseline following treatment for the test and control devices for the following assessments:

- Ocular Surface Staining
- Intraocular Pressure
- BSCVA

Adverse events and other findings shall be summarized by presenting the percentages of subjects with each event type. Continuous endpoints shall be summarized using summary statistics such as means, medians, standard deviations, minima, maxima, and relevant percentiles. Definitions of adverse events, serious adverse events, and categorizations of events can be found in Appendix D.

All adverse events shall be evaluated beginning with onset, and evaluation shall continue until resolution is noted, or until the investigator determines that the subject's condition is stable.

All AEs shall be characterized by the following criteria (see Adverse Event Definitions in Appendix D):

- Event diagnosis
- Intensity or severity (*mild, moderate, severe*)
- Expectedness (anticipated, unanticipated)
- Relatedness to study treatment (*related, not related*)
- Treatment (none, medication, non-drug treatment/procedure, ER visit/hospitalization)
- Action taken (none, study procedure interrupted, study procedure discontinued)
- Outcome (resolved without sequelae, resolved with sequelae-specify, ongoing at time of assessment, death, unknown)

If more than one distinct adverse event occurs, each event shall be recorded separately.

7.2.5.1 Anticipated Adverse Events

- Eyelid/eye Pain
- Eyelid Irritation or Inflammation
- Ocular Surface Irritation or Inflammation
- Ocular Symptoms – Burning, stinging, tearing, itching, discharge, redness, foreign body sensation, visual disturbance, sensitivity to light.

7.2.5.2 Serious Adverse Event and Unanticipated Adverse Device Effect Reporting

SAEs and unanticipated adverse device effects (UADE) must be reported to the study sponsor as soon as possible and no later than 48 hours after the investigator first learns of the event.

For initial reports, Investigators shall record all case details that can be gathered within the reporting timeframe. The contact information for Tear Film Innovations, Inc. below:

Study Sponsor:

Tear Film Innovations, LLC
[name], Chief Executive Officer
[name]
[name]
[contact]
E-Mail: [contact]

Relevant follow-up information shall be submitted to the sponsor as soon as it becomes available and/or upon request. For some events, the sponsor or designee may follow up with the site by telephone, fax, electronic mail, and/or a monitoring visit to obtain additional case details deemed necessary to appropriately evaluate the event (e.g., hospital discharge summary, consultant report, or autopsy report). Reports relating to the subject's subsequent medical course must be submitted to the study sponsor until the event has subsided or, in case of permanent impairment, until the event stabilizes and the overall clinical outcome has been ascertained.

7.2.6 Poolability Analysis

Subject demographic characteristics and background variables shall be summarized. To ensure poolability, primary effectiveness endpoints will be compared across site and gender. Analysis of variance will be used to test mean effects and interaction of stratification variables of treatment. A p-value of 0.15 will be used for these assessments.

7.2.7 Missing Data

Primary and secondary effectiveness endpoints will be imputed when missing to preserve the randomization in the intent-to-treat analysis population. The primary method of imputation used will be by multiple imputation. Ten imputations will be produced for each endpoint using SAS PROC MI. The seed used to begin random number generation will be 11142016. The Markov chain Monte Carlo method will be used to compute with the following predictor variables: baseline tear break-up time, baseline MGS score, gender, and age. Alternate imputation methods used to assess sensitivity to the presence of missing data will be last observation carried forward (LOCF), best case (a test subject's best prior value and a predicate subject's worst prior value is imputed) and worst case (a test subject's worst prior value and a predicate subject's best prior value is imputed). If best case and worst case

conclusions differ, a tipping point analysis will be performed. In the absence of post-treatment data, baseline values will be used for imputation for alternate imputation methods.

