6.2 Subject Withdrawal

Subjects may withdraw their consent to participate in the study at any time, for any reason. Investigators may also withdraw subjects from the study at their discretion in order to protect the rights, safety, or welfare of the subject. All withdrawn subjects will be included in study analyses but they will not be replaced. No missing data will be imputed.

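### The ITT imputation model leaves out treatment arm, which pulls a true iLux deficit toward zero, and section 6.2 rules out imputation altogether

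*Combined protocol and SAP*

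**What the plan says.** Section 7.2.7 states the scope and aim of imputation: "Primary and secondary effectiveness endpoints will be imputed when missing to preserve the randomization in the intent-to-treat analysis population". It continues: "The primary method of imputation used will be by multiple imputation". It specifies ten imputations per endpoint from SAS PROC MI by Markov chain Monte Carlo, a fixed seed, and "the following predictor variables: baseline tear break-up time, baseline MGS score, gender, and age". LOCF, best-case and worst-case imputation are sensitivity analyses, with a tipping-point analysis if the best-case and worst-case conclusions differ.

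Section 6.2 keeps withdrawn subjects in the analyses without replacing them, and then says "No missing data will be imputed". Nothing limits that sentence to a particular population or endpoint.

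Section 7 adds a group certain to have missing outcomes: "Subjects who are randomized but not treated for any reason will be included in the intent-to-treat analysis". These subjects are left out of the per-protocol analysis. Neither population is named as primary for the non-inferiority test. Section 7.2.3 sets the joint rule: "Both co-primary endpoints, MGS and TBUT, must be successful to demonstrate non-inferiority".

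**The concern.** The ANCOVA estimates the difference between arms. If the imputation model does not know the arm, imputed subjects carry essentially no arm difference, and the completed data understate any real one. In a superiority trial that would be conservative. In a non-inferiority trial it moves a truly inferior device toward the inside of the margin, so the chance of a false claim rises above the nominal 2.5%. The stated purpose of imputing is to protect the randomization, yet the model ignores the randomized assignment.

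The clash with section 6.2 is a second problem and does not depend on any missing rate. An ANCOVA of week-4 change cannot include a withdrawn subject with no week-4 value unless something is imputed, so section 6.2 is also hard to carry out as written. With two opposite rules and no named primary population, imputing or not could be decided after the data are seen.

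**Working it through.** **Inputs from the plan.** 128 subjects randomized 1:1, so 64 per arm (section 4.2). MGS margin 5 and SD 8; TBUT margin 2.5 s and SD 4 s (section 7.2.4). ANCOVA on baseline, with success on MGS if the lower confidence limit exceeds -5 (section 7.2.1.1).

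**Reproducing the stated power.** The standard error is 8 × √(2/64) = 1.414, and 5/1.414 = 3.536. Subtracting 1.960 gives 1.576, so power is 94.2% by the normal approximation and 93.9% by the noncentral t with 126 df. This matches the plan. TBUT is identical because 2.5/4 = 5/8. Jointly, 0.939² = 0.882. A one-sided alpha of 0.05 would give 97.1%, so 0.025 is the level in use.

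**Closed form for the shrinkage.** Let a and b be the observed fractions in the two arms, with data missing completely at random and Δ the true difference. Missing values in both arms centre on the pooled observed mean. The expected completed-data difference is

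Δ × 2ab/(a + b),

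which equals Δ × (1 − m) when both arms miss the same fraction m. For m = 10%, -5 × 0.90 = -4.50. If 20% is missing in one arm only, the factor is 2 × 0.8 × 1/1.8 = 0.889, giving -4.44.

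**Missing rate.** The plan gives none after randomization. Its 10% is for something else: "A total of 142 subjects is requested to allow for 10% fallout during patient screening". I therefore assumed 2% to 20%.

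**Simulation.** 64 per arm, SD 8, assumed baseline-outcome correlation 0.3, data missing completely at random and equally in both arms. Bayesian normal regression imputation on the four listed predictors, with or without arm; ten imputations, Rubin's rules, Barnard-Rubin degrees of freedom. True MGS difference -5, 30,000 trials per cell (Monte Carlo standard error about 0.1 percentage point). For the joint columns TBUT is truly equal and the endpoints are assumed independent.

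| Missing | Closed form, no arm | Simulated mean, no arm | MGS error, no arm | MGS error, with arm | Both endpoints, no arm | Both endpoints, with arm |
|---|---|---|---|---|---|---|
| 2% | -4.90 | -4.90 | 2.68% | 2.46% | 2.55% | 2.34% |
| 5% | -4.75 | -4.75 | 2.99% | 2.43% | 2.85% | 2.29% |
| 10% | -4.50 | -4.49 | 3.77% | 2.51% | 3.59% | 2.34% |
| 20% | -4.00 | -3.98 | 5.69% | 2.50% | 5.34% | 2.18% |

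With arm in the model the mean estimate is -5.00 in every row. The single-endpoint figures carry over to TBUT through the equal margin-to-SD ratio. At a true difference of zero (12,000 trials per cell) the mean estimate without arm lies between -0.01 and 0.02, so there is no bias at equality.

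**The case against.** The strongest reply is about size. Randomization happens at the treatment visit, both eyes are treated in one session, and follow-up ends by day 35, so few week-4 values may be missing. At 2% and 5% missing the excess over 2.5% is only about 0.2 and 0.5 percentage points. This stands. The larger figures need 10% to 20% missing. The plan, however, makes no allowance for loss after randomization: the synopsis requires for analysis the same 128 subjects that section 4.2 randomizes.

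Second, the sensitivity analyses could expose a result that hinges on imputation, and the worst case is directed against iLux. That is partly right, but they do not correct the main estimate. A subject with no post-treatment data receives the baseline value under LOCF, best case and worst case alike. Such subjects show zero change in either arm and cannot make the best and worst cases differ, so they cannot trigger the tipping-point analysis. A per-protocol result would be free of the shrinkage, but it is not named as primary.

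Third, sections 4.4.1 and 7 also require a clinically significant iLux change from baseline. In a complete-data check, reading that as an observed mean gain of at least 5, the 2.4% MGS rate falls to 1.9%, 0.8% and 0.1% if LipiFlow's true gain is 9, 8 and 7, and is unchanged at 10 or more. The plan does not give that gain. The tabulated rates are therefore errors of the non-inferiority test and upper bounds on a false claim of overall success.

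Fourth, the shrinkage is symmetric: if iLux is better, its advantage is understated too. And if section 6.2 governs, nothing is imputed and nothing shrinks. Both are true. The second only shows why the conflict has to be settled.

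**Conclusion.** The concern holds on both counts. The predictor list omits the effect being estimated, and under equal, completely random missingness the estimated difference shrinks by the missing fraction. With unequal missingness the retained share is the harmonic mean of the two observed fractions. The resulting error inflation is minor at 5% missing or less and material at 10% to 20%, where the single-endpoint error reaches 3.8% to 5.7%. Requiring both co-primaries does not remove it. The error rates rest on the assumed missing rates, the 0.3 baseline correlation and, for the joint figures, independence of the endpoints. The contradiction between sections 6.2 and 7.2.7 needs no assumption. This should be fixed, though it does not undermine the design.

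**What to change.** - **Section 7.2.7:** add treatment arm to the PROC MI variables, or run PROC MI separately by arm.
- **Section 6.2:** replace the no-imputation sentence with a cross-reference to section 7.2.7, or limit it to named analyses, for example safety and per-protocol.
- **Useful additions, not the cause of the bias:** include the week-2 value of the endpoint. In the simulation (assumed residual correlation 0.6) this left the error at 2.45-2.59%. For OSDI, also include its baseline, since section 7.2.2 says "A similar ANCOVA model will be used to compare OSDI between devices, with covariate adjustment for baseline OSDI" but that covariate is not in the imputation list.
- **Optional:** run the tipping-point analysis on the arm-inclusive imputation whether or not the best and worst cases disagree.

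The cost is one variable or a BY statement, plus two sentences of text. All the data are already collected. Some apparent power is lost: at a true difference of zero, single-endpoint MGS power goes from 95.0% to 93.2% at 10% missing and from 94.2% to 89.2% at 20% missing.
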